## Study Synopsis

Study Title	Ablation efficacy of contact side firing fiber in predefined settings for treating BPH	
Protocol No:	LUM-SBU-VP-15-02	
Device Name:	Lumenis Pulse 120H Holmium Laser system	
Design	Prospective, single arm, single center	
Planned Study period	Initiation: January 2016	Final Report: August 2016
Objectives	
Primary: To explore Vaporization efficacy and safety when treating PBH with the contact side firing fiber with recommended settings
 
Secondary: To demonstrate the usability of BPH treatment with the combined tools Xpedea+ Pulse 120H
	
Study population	Twenty (20) subjects presenting with a hyperplasia enlarged prostate and candidates for surgery	
Main Inclusion Criteria	
 
• Subject will be older than 18 years of age
 
• Subject was diagnosed with enlarged prostate of <math>\geq 30</math> gr volume
 
• Subject is a candidate for surgery treatment
 
• Subject is willing and has signed the Informed Consent Form
 
• AUA score <math>\geq 12</math>
 
• Qmax <math><15</math> mL/s
 
	
Main Exclusion Criteria	
 
• Need to perform concomitant procedure, other than prostate vaporization
 
• PVR <math>> 300</math>mL
 
• Current Urine retention and Pdet <math><40</math> cm H20
 
• Documented or suspected prostate cancer and / or bladder cancer
 
• Neurogenic bladder disorder / neurogenic voiding dysfunction
 
• Urethral strictures
 
• Previous prostatic, bladder neck, or urethral surgery
 
• Known history of spinal cord injury
 
• Urogenital trauma
 
• Bladder neck stricture
 
• Evidence of urinary tract infection
 
• History of chronic prostatitis
 
	
Investigational Treatment and study course	
Following enrollment, each subject will undergo a single treatment for ablation of the prostate. Following treatment subjects will be required to return for follow-up visits at 1 and 3 months.
 
Follow up sessions:
 
 
• Peri-procedure and day of discharge
 
• One month post-surgery
 
• 3 months post-surgery
 
	

**Description: Surgical. Protocol LUM-SBU-VP-15-02, Ablation efficacy of contact side firing fiber in predefined settings for treating BPH**

Criteria for Evaluation (endpoints)	Primary Endpoints: 
 
• Efficacy           
 
• Ablation time
 
• Ablation rate calculated as: Prostate volume measured using pre and post treatment (3 month) TRUS images/ procedure time
 
• Ablation efficacy calculated as: Prostate volume measured using pre and post treatment (3 month) TRUS/ energy used
 
 
 
• Safety:           
 
Intraoperative complications               
 
• Complications according to Clavien scale
 
• Conversion to TURP to maintain hemostasis (procedure completed with laser)
 
• Conversion to TURP to complete procedure
 
• Capsule perforation
 
• Blood loss (blood transfusion, pre and post-operative hemoglobin and hematocrit)
 
 
 
2. Perioperative complications               
 
• Urinary Retention
 
• Haematuria
 
• Dysuria
 
• Infection
 
• Urge incontinence
 
• Stress incontinence
 
• Erectile Dysfunction (International Score as compared to baseline)
 
• Re-catheterization
 
• Readmission for secondary operation
 
 
 
 
 
 Secondary Endpoint: 
 
• Usability:           
 
• Visibility during procedure- subjective assessment
 
• No. of fibers used during procedure
 
• Catheterization time
 
• Hospital stay duration
 
• IPSS QOL (follow-up visits as compared to baseline)
 
• QMax ml/s (follow-up visits as compared to baseline)
 
• PVR (follow-up visits as compared to baseline)
 
• PSA (follow-up visits as compared to baseline)
 
• AUA (follow-up visits as compared to baseline)
 
 
 

--	--

**Description: Surgical. Protocol LUM-SBU-VP-15-02, Ablation efficacy of contact side firing fiber in predefined settings for treating BPH**

## 1 Introduction

### 1.1 Background

The Lumenis Holmium Laser System family has been used for more than a decade for many procedures and specialties requiring excision, incision, ablation, and vaporization of tissue.

The holmium:yittrium–aluminum–garnet (Ho:YAG) laser, known as the holmium laser, is a very commonly used laser in urological surgery [1, **Error! Reference source not found.**]. Its wavelength of 2,120 nm is very near the absorption peak of water (1,910 nm). As a result, it can be used for soft tissue-based applications as well as stone fragmentation. Since soft tissue is comprised primarily of water, the holmium laser energy is effective for excision, incision, ablation, and vaporization when in direct contact with soft tissue, and for coagulation when a few millimeters from soft tissue. If fired directly onto mucosa, the laser has an effective penetration depth of 300–400 micron, thus limiting the collateral injury during tissue-based applications. Additionally, stones (both urinary and gastrointestinal) contain sufficient amount of water that can absorb laser energy leading to their fragmentation, thus facilitating their removal [**Error! Reference source not found.**].

Delivery of holmium laser energy to the target tissue is commonly performed by emitting the energy through flexible hard core fibers of varying diameters. The flexibility of the fibers enables reaching and treating areas that otherwise would have been hard or impossible to reach. Fibers used for soft tissue procedures deliver the laser energy to the desired location by either emitting the laser beam forward (end-fire) enabling excision or to the side (side-firing) used mainly for ablation of tissue.

Benign Prostate Hyperplasia (BPH) endourologic surgery can be performed by either excision of the prostate tissue (Holmium Laser Enucleation of the Prostate – HoLEP) or ablation of the prostate tissue (Holmium Laser Ablation of the Prostate – HoLAP). During the HoLAP procedure, a channel is created within the prostatic fossa to relieve the patient of symptoms secondary to BPH. Side-firing fiber is used to systematically remove superficial layers of the prostate tissue until a cavity is formed. Depending on the prostate volume, this can be a time consuming procedure.

Ablation efficiency during the HoLAP procedure is limited by the laser system output power, transmission loss and the effectiveness of the energy applied to the tissue. The current Lumenis Pules p120H can deliver up to 120W with commonly used energy per pulse of 2-3J at frequencies ranging from 60-30 Hz, accordingly. In order to increase the effective energy per pulse that affects the tissue, any water based interface gap between the fiber and the tissue should be reduced to a minimum. This enables maximum energy to be absorbed directly by the water content of the tissue, leading to ablation. Therefore, using the fiber in direct contact with the tissue during ablation is considered an advantage, particularly in procedures requiring high ablation rate, such as HoLAP.

In order to increase the efficiency of the HoLAP procedures Lumenis has developed several side firing fibers that can be used in contact with the tissue to maximize the laser tissue effect and increase the

**Description: Surgical. Protocol LUM-SBU-VP-15-02, Ablation efficacy of contact side firing fiber in predefined settings for treating BPH**

ablation efficiency of the holmium laser. Together with the powerful tool of the pulse p120H Lumenis offer an efficient and safe combination for HoLAP procedure

This study is intended to quantify the ablation efficiency and the safety of the Xpeeda fiber together with defined settings of the pulse 120H.

## 1.1 Rationale for Evaluation

The Lumenis Pulse P120H enables a wide range of working parameters that include use of high frequency at low energy. The usage of predefined set of parameters for vaporization and coagulations may aid the physician in completing the procedure in a relative short period of time, investing less time and energy with no complications. The combination of side firing fiber together with the pulse 120H is expected to show an effective tool to treat BPH.

## 2 Device Description

### 2.1 Laser System – Lumenis Pulse P120H Holmium Laser

The Lumenis Pulse P120H is a high pulsed solid-state laser used for Urology procedures, worldwide. Importantly, both intended use and indications for use claims as well as underlying laser technology are similar to the marketed product. The activated laser is based on a flash lamp excited, Ho:YAG rod. The Ho:YAG rod derived photons are guided into the attached delivery system fiber. The system delivers a second, low powered laser in the visible wavelength spectrum of 650nm that enables aiming the high, invisible laser energy to the desired location.

### 2.2 Fibers

Xpeeda side firing silica fibers are improved fibers used for laser procedures, to deliver laser energy from the system to the treatment site. The Xpeeda fibers deliver energy directly to the tissue, due to the ability to use it in contact with the tissue during the entire procedure. Xpeeda fibers were design to withstand the high power laser emission of the Lumenis Pulse120H. The Xpeeda fiber is single use, supplied ethylene oxide sterile.

[figure not shown]

Figure 1 – side firing Xpeeda fiber

## 3 Study Design

This is a one arms, prospective, single center study. Subjects will undergo a single treatment for ablation of the prostate using the study device. Follow up visits are scheduled for the day of release

**Description: Surgical. Protocol LUM-SBU-VP-15-02, Ablation efficacy of contact side firing fiber in predefined settings for treating BPH**

from the hospital and at 1 and 3 months post procedure. Additional treatment sessions, if required, will be at the discretion of the investigator, as part of the site standard of practice. Additional sessions will not be included in this study.

## 4 Study Objectives

### 4.1 Primary

To explore Vaporization efficacy and safety when treating PBH with the contact side firing fiber with recommended settings

### 4.2 Secondary

Demonstrate the usability of BPH treatment with the combined tools Xpeda fiber+ Lumenis Pulse 120H system

## 5 Outcome Measures

### 5.1 Primary Endpoints:

#### 5.1.1 Efficacy

- Ablation time
- Ablation rate calculated as: Prostate volume measured using pre and post treatment (3 month) TRUS / procedure time
- Ablation efficacy calculated as: Prostate volume measured using pretreatment and post treatment (3 month) TRUS / energy used

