#### 5.1.2 Safety:

##### 5.1.2.1 Intraoperative complications

- Complications according to Clavien scale
- Conversion to TURP to maintain hemostasis (procedure completed with laser)
- Conversion to TURP to complete procedure
- Capsule perforation
- Blood loss (blood transfusion, pre and post-operative hemoglobin and hematocrit)

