##### 5.1.2.2 2. Perioperative complications

- Urinary Retention
- Haematuria
- Dysuria
- Infection
- Urge incontinence
- Stress incontinence
- Erectile Dysfunction (International Score as compared to baseline)

**Description: Surgical. Protocol LUM-SBU-VP-15-02, Ablation efficacy of contact side firing fiber in predefined settings for treating BPH**

- Re-catheterization
- Readmission for secondary operation

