## 6 Patient Population

### 6.1 Source and Sample Size

Subjects shall be selected by the physician within his patient population. One (1) site will participate in this study and will treat twenty (20) subjects. Enrolled subjects that did not complete the full course of the study will be discarded from performance analysis if they have not returned for the 1 and/or 3 month follow-up visits.

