#### 10.4 Subject Withdrawal/Dropouts

The subjects will be advised in the written Informed Consent form that they have the right to withdraw from the study at any time without prejudice, and may be withdrawn at the Investigator's/Lumenis' discretion at any time. In the event that a subject drops out of the study or is withdrawn from the study, the Exit/Termination CRF should be completed. On the withdrawal page, the Investigator should record the date of the withdrawal, the person who initiated withdrawal and the reason for withdrawal.

Reasonable effort should be made to contact any subject lost to follow-up during the course of the study in order to complete assessments and retrieve any outstanding data and study supplies. The records of subjects who terminate prior to completing the study will be retained and the reason for termination will be documented.

The following are possible reasons for subject dropout/withdrawal:

- Adverse event that would prevent subject compliance with the protocol;
- Subject withdrawal of consent;

However, every effort should be made to see that subject is followed for the remainder of the study even if subject is unable or unwilling to comply with the protocol.

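### If prostate tissue is removed by TURP or by a further operation before the 3-month TRUS, the plan keeps that subject in the primary ablation ratios and has no rule for the extra tissue

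*Combined protocol and SAP*

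**What the plan says.** Two of the three primary efficacy endpoints in section 5.1.1 are ratios built on the same ultrasound volumes. One is "Ablation efficacy calculated as: Prostate volume measured using pretreatment and post treatment (3 month) TRUS / energy used". The other is "Ablation rate calculated as: Prostate volume measured using pre and post treatment (3 month) TRUS / procedure time". The Synopsis gives the same definitions. Neither place writes out the subtraction, says whose energy counts, or says whether procedure time includes time spent on TURP.

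The protocol foresees tissue removal outside the index laser treatment. Section 5.1.2.1 lists "Conversion to TURP to complete procedure" and section 5.1.2.2 lists "Readmission for secondary operation", both as safety endpoints. Section 3 leaves further treatment sessions to the investigator and adds: "Additional sessions will not be included in this study".

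On who is analysed, section 6.1 says that enrolled subjects who do not complete the study are "discarded from performance analysis if they have not returned for the 1 and/or 3 month follow-up visits". Section 10.4 permits withdrawal at the discretion of the investigator or sponsor, but also says that "every effort should be made to see that subject is followed for the remainder of the study". TRUS is scheduled at baseline and 3 months only (Table 1 and Appendix I). Section 8.1 plans a descriptive summary, and neither it nor section 8.2 has a rule for these subjects.

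**The concern.** Numerator and denominator can refer to different treatments. The 3-month volume reflects everything removed by then, while the energy is that of the index laser treatment. The mismatch arises in subjects in whom the laser did not finish the job or who needed more treatment, and for volume per energy it moves the recorded result in the device's favour.

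Section 1.1 (Background) says the study is meant to quantify ablation efficiency for this fiber at defined settings, so the ratio is close to the study's purpose. Without a rule, the handling of an affected subject could be settled after the results are known. A reader could see that a conversion happened without knowing whether it entered the efficacy mean.

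**Working it through.** **Reading the text.** Take a subject converted to TURP to complete the procedure who attends both visits.

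1. Section 6.1 does not discard this subject, because no visit was missed.
2. Section 10.4 favours continued follow-up, and withdrawal is discretionary.
3. Section 3 deals with additional sessions, not with TURP inside the index procedure.
4. No ultrasound is scheduled between the laser work and the TURP, so a laser-only volume cannot be recovered from the schedule.

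For an additional session, section 3 puts the session outside the study. It does not say what happens to the subject or to a TRUS taken afterwards. If only the session is left out, its energy is missing from the denominator while its tissue stays in the numerator.

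**Size.** The plan gives no expected ratio, event rate or volume, so there is no figure to reproduce. Section 9.3.2 describes complications only as very infrequent. The sole planning input is 20 subjects (section 6.1). All other inputs below are assumptions.

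*Volume per energy.* Let f be the extra tissue as a multiple of the laser-removed volume, and k the number of affected subjects. If their laser efficiency matches the others, the mean is inflated by k × f / 20.
- k = 0: 0%.
- k = 1, f = 0.5 to 1.0: 0.5/20 to 1.0/20 = 2.5 to 5%.
- k = 2: 5 to 10%.
- k = 1, with three quarters of the total reduction removed by other means (f = 0.75/0.25 = 3): 15%.

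*Chance of a case.* With per-subject risk p, the chance of at least one case is 1 − (1 − p)^20. Expected inflation is p × f, for f = 0.5 to 1.0.

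| p | At least one case | At least two cases | Expected inflation |
|---|---|---|---|
| 1% | 18% | 2% | 0.5 to 1% |
| 2% | 33% | 6% | 1 to 2% |
| 5% | 64% | 26% | 2.5 to 5% |

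*Volume per procedure time.* Assume 60 minutes of laser work, with TURP adding t minutes that count as procedure time. The subject's ratio changes by (1 + f)/(1 + t/60) − 1.
- f = 0.5, t = 15, 30, 45: +20%, 0%, −14.3%.
- f = 1.0, t = 15, 30, 45: +60%, +33.3%, +14.3%.

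Divided by 20, one conversion moves the mean by −0.7% to +3%. A later operation that removes tissue adds no index procedure time, so its effect is again +2.5 to +5%.

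*Would exclusion cure it?* Suppose one converted subject's laser-only volume per energy is lower than the others' by a fraction d. Setting the others to 1, the true mean is (20 − d)/20. Dropping the subject gives a bias of d/(20 − d). Keeping the recorded value gives (1 − d)f/(20 − d).

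| d | Dropped | Kept, f = 0.5 | Kept, f = 1.0 |
|---|---|---|---|
| 0 | 0% | +2.5% | +5.0% |
| 0.25 | +1.3% | +1.9% | +3.8% |
| 0.50 | +2.6% | +1.3% | +2.6% |
| 0.75 | +3.9% | +0.6% | +1.3% |

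Dropping is worse than keeping when d > f/(1 + f): above 33% for f = 0.5 and above 50% for f = 1.0.

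**The case against.** The strongest reply is that little depends on this. The aim is exploratory (section 4.1), the analysis is descriptive with no threshold or comparator, and every size above is assumed. Conversions and secondary operations are themselves primary safety endpoints, and section 8.2 puts all endpoints in one final report, so readers of a 20-subject series would see how many occurred. This stands, and it limits the point to a minor correction. It does not tell the reader whether those subjects are in the efficacy mean.

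A second reply is that section 3 already keeps data after an additional session out of the results. That is a possible reading for later sessions, but the sentence does not mention the subject or the TRUS, and it cannot cover TURP at the index procedure.

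Third, energy used is not defined as laser energy only. That is correct. The point rests on the natural reading, and the definition should be written down.

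A reader might also infer that affected subjects should simply be removed from the headline ratio. The plan gives no basis for that. A subject converted to complete the procedure may be one in whom the laser underperformed, and the last table shows that dropping such a subject can bias the mean more than keeping the recorded value.

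**Conclusion.** The gap is real but conditional. Followed as written, the formulas and the discard rule keep an affected subject in both primary ratios. Volume per energy is then too high for that subject. Volume per procedure time may be too high or too low after a conversion.

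One case in 20 raises the mean volume per energy by about 2.5 to 5%, assuming extra tissue of 0.5 to 1.0 times the laser volume and laser efficiency equal to the others'. The rise is smaller if that efficiency was lower, larger if other means removed most of the tissue, and zero if no case occurs.

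A reader might go further and conclude that the study will credit non-laser tissue to the laser. The documents do not support that. They give no event rate. A secondary operation need not remove prostate tissue, an additional session could itself use a laser, and a conversion for hemostasis may resect little or nothing. No test or success criterion is affected. This is a minor correction to the definition and reporting of two primary endpoints.

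**What to change.** In sections 5.1.1 and 8.1:

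- State that ablated volume is baseline minus 3-month TRUS volume, and that energy used is the laser energy of the index procedure.
- Report both ratios for all subjects with a 3-month TRUS, and again without those who had prostate tissue removed before that TRUS by means other than the index laser treatment. Give the two versions equal prominence.
- Show the number of such subjects out of 20 beside the ratios, with a note that either version may favour the device.
- State that a subject converted for hemostasis only, with no tissue resected, stays in both versions.

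On the CRF, record whether tissue was resected, and the date and type of any additional session. Add a cross-reference in section 3 and a matching line in section 6.1, whose discard wording can be read as dropping a subject who missed only the 1-month visit.

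The cost is a few sentences, a second set of summary figures and a few CRF items. Conversions are already endpoints, and section 9.1.3 already has onset date and additional treatment recorded for adverse events. Sample size, visits and patient management do not change.

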#### 5.1.2 Safety:

##### 5.1.2.1 Intraoperative complications

- Complications according to Clavien scale
- Conversion to TURP to maintain hemostasis (procedure completed with laser)
- Conversion to TURP to complete procedure
- Capsule perforation
- Blood loss (blood transfusion, pre and post-operative hemoglobin and hematocrit)

##### 5.1.2.2 2. Perioperative complications

- Urinary Retention
- Haematuria
- Dysuria
- Infection
- Urge incontinence
- Stress incontinence
- Erectile Dysfunction (International Score as compared to baseline)

**Description: Surgical. Protocol LUM-SBU-VP-15-02, Ablation efficacy of contact side firing fiber in predefined settings for treating BPH**

- Re-catheterization
- Readmission for secondary operation

## 5.2 Secondary Endpoint:

### 5.2.1 Usability:

- Visibility during procedure
- No. of fibers used during procedure
- Catheterization time
- Hospital stay duration
- IPSS QOL (follow-up visits as compared to baseline)
- QMax ml/s (follow-up visits as compared to baseline)
- PVR (follow-up visits as compared to baseline)
- PSA (follow-up visits as compared to baseline)
- AUA score (follow-up visits as compared to baseline)

## 6 Patient Population

### 6.1 Source and Sample Size

Subjects shall be selected by the physician within his patient population. One (1) site will participate in this study and will treat twenty (20) subjects. Enrolled subjects that did not complete the full course of the study will be discarded from performance analysis if they have not returned for the 1 and/or 3 month follow-up visits.

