## 7 Study Procedures

### 7.1 Study duration and timelines

For each subject the duration of the study will be of 3 months. Subjects may remain hospitalized following surgery, based on physician's discretion. Subjects will be followed at the day of their discharge from the hospital. Each subject will return for follow-up visits at 1 and 3 months following the treatment procedure at which time they will have completed their participation in the study.

It is expected that enrollment of all study subjects at the site will occur within 12-16 weeks from study initiation.

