#### 7.2.2.5 Investigator Subjective Assessments

**Description: Surgical. Protocol LUM-SBU-VP-15-02, Ablation efficacy of contact side firing fiber in predefined settings for treating BPH**

Revision: B  
 State: Released  
 ECO No: GEN-0007426  
 Effective Date: 02-Jun-2016

7.2.2.6 Procedure Questionnaire will record subjective usability parameters including visibility impairment and resolution (due to bleeding or other disturbances), fiber positioning, vaporization control and ability to successfully complete the procedure.

Table 1 – Assessments time-points:

Assessment	Baseline (Pre- operative)	Performed During Visit			
		Perioperative	Hospital discharge	1 month follow- up	3 month follow- up
Subject assessment (ICF, medical history, demographics, inclusion/exclusion evaluation)	X				
Trans Rectal Ultrasound	X				X
Post Void Residual Ultrasound	X			X	X
Q-Max Uroflow	X			X	X
Urodynamic Evaluation	X				
Blood analysis (CBC, BMP & PSA) & urine analysis	X	X (CBC)			X
Urine culture (if applicable)	X				X
Erectile Dysfunction	X				X
Subject Questionnaires (AUA, QoL)	X			X	X
Physician Subjective Procedure Questionnaire		X			
Adverse Event Assessment		X	X	X	X

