# **8 Study Analysis Plan**

## **8.1 Study Analysis**

The results of the study: subject demographics, baseline assessments, treatment parameters, treatment evaluations and follow-up assessments will be summarized and descriptive analysis will be performed. Adverse events reported will be listed, documenting course, outcome, severity, and possible relationship to the treatment. The modified Clavien classification will be used to evaluate severity of Adverse Events [2].

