## **8.2 Interim report**

Interim analysis of the immediate post-operative data will be performed after at least 10 subjects underwent surgery in order to assess the immediate study results. If applicable, most of the study endpoint analysis will be performed for the initial 10 patients including ablation duration, safety parameters and secondary end-points (if applicable according to follow-up scheduled). Treatment

**Description: Surgical. Protocol LUM-SBU-VP-15-02, Ablation efficacy of contact side firing fiber in predefined settings for treating BPH**

safety and adverse events report, durations and all endpoints will be analyzed following the completion of all study subjects follow-up period and summarized in the final report.

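### Section 6.1 drops non-completers from an undefined performance analysis; if that covers efficacy, it discards observed ablation times and, read literally, ablation rate and efficacy as well

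*Combined protocol and SAP*

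**What the plan says.** Section 6.1 plans 20 treated subjects at one site and sets the only rule on who is analysed. It applies to "Enrolled subjects that did not complete the full course of the study" and says that they "will be discarded from performance analysis if they have not returned for the 1 and/or 3 month follow-up visits". The term *performance analysis* occurs nowhere else.

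Section 7.1 describes return visits at 1 and 3 months, "at which time they will have completed their participation in the study".

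Section 5.1.1 lists three primary efficacy endpoints. Ablation time is a procedural measurement. The second is "Ablation rate calculated as: Prostate volume measured using pre and post treatment (3 month) TRUS / procedure time". The third, ablation efficacy, has the same ultrasound inputs with energy used in place of procedure time. In Table 1 the row "Trans Rectal Ultrasound" is marked at baseline and 3 months, not at 1 month. Appendix I repeats this.

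Section 8.1 says that "treatment parameters, treatment evaluations and follow-up assessments will be summarized and descriptive analysis will be performed". Section 8.2 says that "durations and all endpoints will be analyzed following the completion of all study subjects follow-up period". Neither defines an analysis set. Section 10.4 asks for reasonable effort to contact subjects lost to follow-up "in order to complete assessments and retrieve any outstanding data and study supplies".

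**The concern.** An exclusion rule should match the data that each endpoint needs. This one is tied to visit attendance, and it points to an analysis that is not defined. One analyst could apply it to all efficacy and usability summaries, another to the functional outcomes only. One could count a subject seen at month 3 but not at month 1 as a completer, another could not. Each could claim to follow the protocol, and they would report primary efficacy on different subjects.

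At stake are precision in a sample of 20 and the possibility that the efficacy summaries describe a selected group, since section 10.4 names an adverse event as a possible reason for dropout. The study tests no hypothesis, so power and type I error are not involved.

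**Working it through.** The sample size of 20 comes with no dropout rate, variance or precision target, so there is no planned figure to reproduce. The check matches each endpoint's data needs to the visit schedule.

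**Step 1: what is observed.** Inputs are sections 5.1.1 and 5.2.1 and Table 1, assuming that every other assessment was done. Ablation time, number of fibers, catheterization time and hospital stay have no row in Table 1; their timing is inferred from what they measure. For ablation time section 8.2 supports this, because the interim analysis takes ablation duration from immediate post-operative data.

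| Endpoint | Misses month 3 only | Misses month 1 only | Misses both |
|---|---|---|---|
| Ablation time (primary) | observed | observed | observed |
| Ablation rate, ablation efficacy (primary) | not available | observed | not available |
| Fibers, visibility, catheterization time, hospital stay | observed | observed | observed |
| QoL, Qmax, PVR, AUA | 1-month value | 3-month value | none |
| PSA | not available | observed | not available |

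Primary efficacy endpoints observed: 1 of 3, 3 of 3 and 1 of 3. None uses month-1 data; two use month-3 data.

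**Step 2: what the rule discards, if it covers efficacy.**

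- Literal reading (one missed visit is enough): all three columns. Observed primary endpoints lost per subject: 1, 3 and 1.
- Alternative reading (attending month 3 completes the course): first and third columns only. Observed primary endpoints lost per subject: 1, 0 and 1.

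The loss of ablation time for a subject without a month-3 visit is common to both. If usability is also covered, the fiber count, visibility, catheterization time, hospital stay and any 1-month values go too.

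**Step 3: size without a dropout assumption.** Each subject is 1/20 = 5% of the sample. With a constant SD, dropping 1, 2 or 4 of 20 observed ablation times multiplies the standard error of the mean by √(20/19) = 1.026, √(20/18) = 1.054 or √(20/16) = 1.118.

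**Step 4: illustration with assumed miss rates.** Let p be the probability of missing each visit. The values are assumptions; the documents give none.

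| p | Have 3-month TRUS, 20(1−p) | Kept, literal rule, misses never coincide, 20(1−2p) | Kept, literal rule, independent misses, 20(1−p)² | Kept, literal rule, misses fully overlap, 20(1−p) |
|---|---|---|---|---|
| 5% | 19 | 18 | 18.05 | 19 |
| 10% | 18 | 16 | 16.2 | 18 |
| 15% | 17 | 14 | 14.45 | 17 |

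Subjects lost for month 1 alone are the second column minus the kept number: 0 to 1, 0 to 2 and 0 to 3. The number is 0 if nobody who misses month 1 returns at month 3, and 0 under the alternative reading.

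At p = 10% under the literal rule, the standard error of mean ablation rate is multiplied by between √(18/18) = 1 and √(18/16) = 1.061. That of mean ablation time is multiplied by between √(20/18) = 1.054 and √(20/16) = 1.118. Under the alternative reading the factors are 1 and 1.054.

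**The case against.** The strongest objection concerns the subject who misses only month 1. Section 6.1 first restricts the rule to non-completers and then adds the visit condition. Section 7.1 can be read as making the month-3 visit the point of completion, and section 10.4 describes non-completers as people who drop out, withdraw or terminate early. On that reading *and/or* still does work: leaving before month 1 misses both visits, and leaving between the visits misses only month 3. This stands as a tenable reading. A reader might infer that the protocol certainly discards subjects with complete primary efficacy data; the text does not settle that. The objection does not reach the loss of ablation time after a missed month 3.

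A reader might also infer that sections 8.1, 8.2 and 10.4 contradict 6.1. They do not. The first two say what is summarized and when, without naming a population. The third concerns retrieving data, which is compatible with analysing completers only.

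It is also fair to say that a single completer set is a legitimate, if less efficient, choice for a small exploratory study, and that the practical effect may be nil. The first does not answer why a procedural measurement should depend on a later visit. The second limits the weight of the point.

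**Conclusion.** The point holds in conditional form. If *performance analysis* covers the efficacy endpoints, section 6.1 discards observed primary data: ablation time for any subject who drops out before month 3, on every reading of completion; and ablation rate and ablation efficacy for a subject who misses only month 1, on the literal reading alone. If the term does not cover efficacy, no primary efficacy value is lost, but the protocol then leaves the population for those endpoints unstated.

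The effect is a possible loss of precision and possible completer selection. The number of subjects affected cannot be derived and may be zero; neither can the size or direction of any selection bias. The documents do not support a claim that bias has been shown. Nor do they support reading the rule as limiting adverse event reporting to completers: section 8.1 lists reported events without that restriction, and section 10.4 asks for every effort to follow such subjects. The point is modest, but it concerns an actual exclusion rule, and a better one is available at almost no cost.

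**What to change.** Replace the exclusion sentence in 6.1 with endpoint-specific sets, repeat them in 8.1, and settle them before the data are analysed:

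- (a) All treated subjects: ablation time, number of fibers, visibility, catheterization time, hospital stay, complications and adverse events.
- (b) All subjects with a baseline and a 3-month TRUS, whether or not the 1-month visit took place: ablation rate and ablation efficacy.
- (c) All subjects with a baseline value and the relevant visit's measurement: Qmax, PVR, AUA and QoL at 1 and 3 months; PSA and the erectile function score at 3 months.

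Section 5.1.2.2 lists erectile dysfunction among the complications, so say that its score change is summarized in set (c). Report n and the reasons for missing data for each endpoint. The completer set may be kept as a sensitivity analysis.

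The cost is one paragraph of text in each of the two sections, with no extra visits, data or subjects. The n will differ between tables, and bias from a missing 3-month TRUS remains under any of these sets.
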